12.7 Cooperative Research and Development Agreement (CRADA)/Clinical Trials Agreement (CTA)

Not Applicable

13. STATISTICAL CONSIDERATIONS

13.1 Study Design/Description

This is a pilot study designed to assess the effect of erlotinib on participants with cirrhosis in trying to prevent hepatocellular carcinoma (HCC). The primary objective of this study is to determine the minimum effective dose (MED) of daily erlotinib that inhibits EGFR signaling in the target organ (liver) as assessed by phospho-EGFR staining. Statistical considerations regarding sample size are based on this primary study objective. Specifically, we will find the minimum effective dose (MED) that achieves at least a 40% response rate, **where a response is defined as a reduction of at least 50% in liver phospho-EGFR staining, defined as the percentage of positive pixels from baseline in an evaluable participant after a 7-day intervention period with daily erlotinib.**

The secondary endpoint of adverse events will assess the overall adverse event rates and specific adverse events for erlotinib over the 7 day intervention period. Translational endpoints are listed in Sections 1.3 and 8.3.

There is limited Quality of Life (QOL) data on participants who participate in chemoprevention trials and we intend to create a databank of QOL information by administering the “Was It Worth It” (WIWI) questionnaire at trial completion across multiple trials. We will seek to evaluate participant perception of their experience in trial participation once we have a reasonable amount of information (large enough sample size). Since participants who participate in these chemoprevention trials are high risk but otherwise healthy, the WIWI tool would help answer simple questions about participants’ assessment of whether or not participation in this trial was “worth it.”

13.2 Randomization/Stratification

Given that this is a single arm pilot trial of erlotinib, there will be no randomization or stratification.

13.3 Accrual and Feasibility

Ten participants will be enrolled (in cohorts of 5) at each dose level to reach the goal of 5 evaluable participants in each dose level using a cohorts-of-5 design. This assumes that 30%-40% of participants will not be evaluable for the primary endpoint for the surgical cohort, have no phospho-EGFR staining (i.e. no positive pixels, see Section 9.0) at baseline, for both cohorts, will otherwise be non-evaluable (drop-out, non-compliant etc.). Assuming that 10 participants are required at each dose level (to achieve the desired 5 evaluable participants), and assuming the theoretical maximum of 3 dose levels, a total of 30 participants may be required for the dose escalation phase to determine the MED. An additional 15 participants will be accrued to the MED in the expansion cohort, wherein we again assume that 30%-40% of participants will not be evaluable for the primary endpoint (see rational above), thus leading to 10 evaluable participants. See section 13.6 for the details on criteria for evaluability of primary endpoint. Thus, the maximum accrual to this trial may be 45 (30 for dose escalation and 15 for the expansion) in order to accrue 25 evaluable participants.

Update with Amendment 9: Because there were no dose-limiting toxicities and there were sufficient numbers of evaluable participants, none of the cohorts were repeated. The target accrual has been adjusted from the original “up to 65” downward to 31. The accrual time frame is limited due to the imminent expiration of the supply of study agent.

13.4 Primary Objective, Endpoint(s), Analysis Plan

The primary objective of this study is to determine a safe and minimum effective dose (MED) of daily erlotinib that inhibits EGFR signaling in the target organ (liver) as assessed by phospho-EGFR staining.

We have no data to demonstrate that this will be different between the surgical and non-surgical cohorts, thus the primary endpoint will be analyzed overall, including data from both cohorts. The primary endpoint is to find the safe and MED that achieves a response rate of at least 40%, where a response is defined as an evaluable patient that achieves a 50% reduction in the percentage of positive pixels in the phospho-EGFR staining in the liver from baseline after a 7 day intervention period with daily erlotinib. See Section 13.6 for criteria for the evaluability of the primary endpoint.

Assuming a binomial distribution for the number of responses in 5 evaluable participants at a given dose level, and a true response rate of 60%, the probability of observing at least 2 responses is 91%. We felt this was adequate evidence of activity in a small pilot study (see table below with the details), given that a true response rate of 60% could not be ruled out even if we only observe a 40% response rate.

Number of responses (x)	P(x)
0	0.010
1	0.077
2	0.230
3	0.346
4	0.259
5	0.078

In summary, we will find the MED that achieves a 40% or higher observed response rate in participants that have at least some EGFR staining at baseline.

Once the MED is determined, we will expand accrual at that dose level to a total of 20 participants (to obtain 10 evaluable) to further evaluate the safety and response rate along with other translational endpoints at that dose level.

With 10 evaluable participants, we would be able to develop a 2-sided 90% confidence interval with a margin of error of about 25% for the response rate endpoint. Given that this is a pilot study, we would use the information we gain from the primary and secondary/translational endpoints to plan for a larger study that would further evaluate this treatment in this disease setting.

13.5 Secondary and Translational/Exploratory Endpoints

The secondary endpoint is to assess the complete adverse event profile for erlotinib.

Translational endpoints consist of the following:

- To assess the relationship between dose-level and staining of phospho-ERK, PCNA, EGF, and α SMA in the liver
- To assess relationship between dose and modulation of a gene expression signature associated with prognosis in cirrhosis.
- To determine whether erlotinib is associated with a measurable reduction in viral load in participants with HCV+.
- To determine the relationship between erlotinib dose-schedule and erlotinib plasma level on the day of liver resection.

Analysis Methods: The translational endpoints will be assessed from tissue samples. Data for these translational endpoints will be considered hypothesis generating and/or exploratory in nature. We will compare the baseline biomarker expression levels (e.g. staining of phospho-ERK, PCNA and α SMA; gene expression signature; viral load) across all the dose levels using analysis of variance (ANOVA) or the nonparametric equivalent. We will also assess the changes in these biomarker values from baseline to Day 7 using the Wilcoxon Signed-Rank test and compare these changes across dose levels using ANOVA (or the nonparametric equivalent). Graphical methods will also be used to assess the differences in these biomarker values across dose levels. All categorical variables will be analyzed using chi-square or Fisher's exact tests.

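### Section 13.5 compares biomarker changes across dose levels without baseline adjustment or interval estimates, and a signed-rank test on 5 pairs within one level could not go below an exact two-sided p of 0.0625

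*Combined protocol and SAP*

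**What the plan says.** Section 13.5 of the combined protocol and SAP gives the analysis of the translational endpoints in one paragraph with three parts.

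- Baseline across dose levels: "We will compare the baseline biomarker expression levels", by ANOVA or the nonparametric equivalent.
- Change within participants: "We will also assess the changes in these biomarker values from baseline to Day 7 using the Wilcoxon Signed-Rank test".
- Change across dose levels: ANOVA of those changes, or the nonparametric equivalent, supported by graphics.

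The section calls these data exploratory or hypothesis generating. It gives no alpha, sidedness, choice of exact or approximate p-value, or scale for the change. It does not say whether the signed-rank test is run per dose level or over all levels. It names no covariate and promises no confidence interval.

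The group sizes come from Sections 13.3 and 13.4. Section 13.3 says: "Ten participants will be enrolled (in cohorts of 5) at each dose level to reach the goal of 5 evaluable participants in each dose level". The full plan is reached "assuming the theoretical maximum of 3 dose levels", plus an expansion at the MED, "in order to accrue 25 evaluable participants". Section 13.4 says the expansion is meant "to further evaluate the safety and response rate along with other translational endpoints at that dose level". The Amendment 9 update in Section 13.3 adds: "The target accrual has been adjusted from the original “up to 65” downward to 31".

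**The concern.** The translational endpoints ask how each marker relates to dose. Section 13.4 says that the primary, secondary and translational results will be used to plan a larger study. For that purpose the useful output is the size of the change at each dose with its uncertainty, and Section 13.5 does not commit to producing it.

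Two features of the named tests make this worse. First, if the signed-rank test is applied within a level of 5, it cannot cross the conventional two-sided 5% line however consistent the fall is, and a p-value of 0.0625 could be misread as no effect. Second, the comparison across levels uses change without adjusting for the starting value, which discards precision when the groups are very small. The plan compares baselines separately but does not say what follows from the result.

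**Working it through.** **Inputs.** From the documents: 5 evaluable per dose level from 10 enrolled, 30% to 40% not evaluable, at most 3 levels, 10 evaluable in the expansion, 25 evaluable in all (Section 13.3). Assumed, because the documents do not give them: a two-sided 5% level, the pre/post correlation rho, equal pre and post SDs, and the effect sizes.

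**1. The plan's own figure at n = 5.** Section 13.4 gives 91% for at least 2 responses in 5 at a true rate of 60%. Check: 1 − 0.4^5 − 5 × 0.6 × 0.4^4 = 1 − 0.0102 − 0.0768 = 0.913. It reproduces. Section 13.5 states no operating figure for the marker tests.

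**2. Signed-rank floor.** With n non-zero pairs all in one direction, the exact two-sided p-value is 2/2^n.

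| n pairs | Minimum exact two-sided p |
|---|---|
| 4 | 0.125 |
| 5 | 0.0625 |
| 6 | 0.031 |
| 7 | 0.016 |
| 10 | 0.002 |
| 15 | 0.00006 |

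At n = 5 the one-sided minimum is 0.031. The normal approximation gives 0.043 two-sided without continuity correction and 0.059 with it. The floor therefore bites only for an exact, two-sided test on 5 or fewer pairs.

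**3. How often a level has 5 or fewer pairs.** Ten enrolled with 30% to 40% loss gives an average of 6 to 7 evaluable. The binomial chance of 5 or fewer out of 10 is 15% at 70% evaluable and 37% at 60%. Under Section 7.4.3, a safe level with at least 40% responders can also stop at its first 5 participants if all are evaluable. HCV RNA is measured only in HCV-positive participants, so its groups will usually be smaller. At the MED, Section 13.3 implies 5 + 10 = 15 evaluable. Section 13.4 can be read as a total of 10. Either number clears the floor.

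**4. What is lost at n = 5.** Exact two-sided signed-rank power at 5% is 0%. A paired t-test (4 df, noncentral t) has 71% power at a mean change of 1.5 SD of the changes and 91% at 2 SD.

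**5. Baseline adjustment.** With equal pre and post variance (set to 1), the variance of a change is 2(1 − rho), and the residual variance after adjusting for baseline is 1 − rho². The ratio is (1 + rho)/2, which is 0.65, 0.75 and 0.85 at rho 0.3, 0.5 and 0.7.

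Simulated power for three levels, two-sided 5%, no baseline differences between levels:

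| Sizes; assumed effects (SD) | rho | ANOVA of change | Baseline-adjusted |
|---|---|---|---|
| 5/5/5; 0, −0.75, −1.5 | 0.3 | 34% | 44% |
| | 0.5 | 45% | 52% |
| | 0.7 | 67% | 71% |
| 5/5/15; −1.2, −0.6, 0 | 0.3 | 38% | 52% |
| | 0.5 | 50% | 61% |
| | 0.7 | 73% | 78% |

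With no dose effect, both methods reject about 4% to 5.5%.

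**6. The risk on the other side.** Sizes 5/5/15, no change in any group, but stable baseline differences between levels. With differences of 1/0.5/0 SD, ANOVA of change rejects about 5%. The adjusted model rejects about 18% at rho 0.3, 13% at 0.5 and 9% to 10% at 0.7. With differences of 0.4/0.2/0 SD, the adjusted model rejects about 6% to 8%.

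**The case against.** **The plan may never run the test that has the floor.** Section 13.5 does not call for an exact, two-sided test at 5% within each level. The sentence reads equally well as one pooled pre/post test followed by a comparison across doses. This stands. A reader might infer that the named test can never reach p < 0.05 in this trial, and the documents do not support that. What remains is that the section does not say which test is meant.

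**The 5 belongs to the primary endpoint.** It is the goal for participants evaluable for phospho-EGFR. Someone not evaluable for that may still supply other markers, and the plan's own loss rate implies 6 to 7. This also stands, although step 3 shows that 5 or fewer is not rare.

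**Baseline is not ignored.** It enters every change and is compared across levels. A reader might infer that the plan disregards it, or that it specifies absolute changes. Neither is in the text: the gap is the missing covariate, and the scale is simply not stated.

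**Adjustment is not automatically safer here.** Section 13.2 rules out randomization and the levels fill in sequence, so change scores and adjusted values can answer different questions. Step 6 supports this. It is the reason to keep the baseline comparison and to report both analyses.

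**One log-scale model does not suit every marker.** Positive-pixel fractions can be zero and HCV RNA can be undetectable. The signature result in Section 9.1 is a per-participant prediction with a confidence p-value. The specimen chart in Section 10.2 shows screening cores in RNAlater for the surgical cohort only, so a like-for-like signature baseline may be missing in the non-surgical cohort. This stands and narrows the fix.

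**Conclusion.** The concern holds in limited form. Section 13.5 leaves the scope of the signed-rank test open, compares changes across dose levels without baseline adjustment, and commits to no estimates with intervals. A test within a level on 5 pairs could not go below an exact two-sided p of 0.0625. That limit is absent in a pooled test, at the expanded MED level, and wherever there are 6 or more pairs.

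The planned ANOVA of changes is not invalid; in step 5 it held its error rate. Its cost is precision. In the scenarios shown, power rises with adjustment by about 4 to 14 percentage points, most when rho is low. These gains rest on an assumed rho, equal pre and post SDs, assumed effects and comparable baselines.

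A reader might infer that the dose decision is at risk. It is not: the MED rule uses the phospho-EGFR response and safety, and the analyses at issue are declared exploratory with no significance threshold. Severity is minor.

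**What to change.** Amend Section 13.5 as follows.

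1. For the continuous markers (phospho-ERK, PCNA, EGF and αSMA staining, and HCV RNA where numbers allow), compare dose levels with a model of the post-intervention value on the baseline value plus dose level. State the scale for each marker and the rule for zero or undetectable values.
2. Report the adjusted change at each dose level with a 95% confidence interval.
3. Use the signed-rank test for all dose levels combined, and state its sidedness and whether the p-value is exact.
4. Keep the comparison of baselines across levels as a description, and report the unadjusted change as a sensitivity analysis, because the levels fill sequentially without randomization.
5. Analyse the gene-signature call separately, as a per-participant classification.

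The cost is SAP wording with no new data. Statistically it is one degree of freedom and a common-variance assumption, with possible bias if dose groups differ stably at baseline; items 4 and 2 together let a reader see that. The size of the gain will not be known until the pre/post correlation is observed.

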1. OBJECTIVES

Primary Objective: Determine the safe and minimum effective dose (MED) of daily erlotinib that inhibits epidermal growth factor receptor (EGFR) signaling in the target organ (liver) as assessed by phospho-EGFR staining.

Secondary Objective: Determine the relationship between erlotinib dose-schedule and side effects in participants with cirrhosis.

Translational Objectives:

1. Determine the relationship between erlotinib dose-schedule and immuno-histochemical staining pattern of phospho-ERK, proliferating cell nuclear antigen (PCNA), epidermal growth factor (EGF), and alpha Smooth Muscle Actin (α SMA) in the liver.
2. Determine the relationship between erlotinib dose-schedule and gene expression signature associated with prognosis in cirrhosis participants following hepatocellular carcinoma (HCC) resection.
3. Determine the relationship between erlotinib dose-schedule and viral load in participants with HCV+.
4. Determine the relationship between erlotinib dose-schedule and erlotinib plasma level on day of liver resection.

1.1 Primary Endpoint: To find the safe and minimum effective dose (MED) that achieves at least a 40% response rate, where a response is defined as an evaluable participant that achieves a reduction of at least 50% from baseline in liver phospho-EGFR staining, defined as the percentage of positive pixels, after a 7-day intervention period with daily erlotinib.

1.2 Secondary Endpoint: To assess the complete adverse event profile for erlotinib.

1.3 Translational/Exploratory Endpoints:

1. To assess the relationship between dose-level and staining of phospho-ERK, PCNA, EGF, and α SMA in the liver.
2. To determine the relationship between erlotinib dose-schedule and gene expression signature previously demonstrated to be associated with prognosis in cirrhosis patients following HCC resection.
3. To determine whether erlotinib is associated with a measurable reduction in viral load in participants with Hepatitis C (HCV+).
4. To determine the relationship between erlotinib dose-schedule and erlotinib plasma level on the day of liver resection.

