- A rat model of progressive fibrosis and cirrhosis induced by repeated, low-dose diethylnitrosamine (DEN) was demonstrated to closely resemble the histopathologic, physiologic, and molecular features observed in human cirrhosis. A global human cirrhosis gene expression signature was developed by comparing 10 normal livers to 13 cirrhotic livers using a publicly available dataset (GEO accession number GSE6764). Strong enrichment of the human signature in the DEN-treated rat livers was observed, indicating that the rat model indeed recapitulates global transcriptional dysregulation observed in human cirrhosis. And EGF was demonstrated to activate hepatic myofibroblasts/hepatic stellate cells (HMF/HSC), which are the key effector cells that promote liver fibrogenesis.
- Administration of clinically-achievable doses of an EGF receptor (EGFR) antagonist erlotinib to rats with DEN-induced cirrhosis suppressed the EGFR pathway as assessed by measurements of phosphoEGFR and other downstream signals in the liver, decreased HMF/HSC activation, reduced fibrogenesis and prevented progression of cirrhosis and subsequent HCC (7). Histologic examination of liver sections stained by H&E and trichrome revealed a lesser severity of fibrosis and cirrhosis in erlotinib treated rats. The reduction of DEN-induced fibrogenesis associated with erlotinib was dose-dependent. Erlotinib-treated rats had significantly lower Ishak fibrosis scores compared to vehicle controls. Moreover, erlotinib reduced the score in some animals, indicating reversal of fibrosis. Erlotinib improved rat liver function as assessed by serum ALT, AST, alkaline phosphatase, total bilirubin, and glucose. The 73-gene poor-prognosis signature in erlotinib-treated vs. control animals was diminished in a dose-dependent fashion in response to erlotinib. Similarly, the 113-gene good-prognosis signature was increased in a dose-dependent fashion in erlotinib-treated vs. control animals.
- In addition to reducing fibrogenesis and improving liver function, erlotinib treatment significantly decreased the number of HCC tumors detectable at week 18 post DEN exposure. Control animals harbored 20.4 ± 5.5 tumors, whereas erlotinib at 2 mg/kg and 0.5 mg/kg harbored only 5.0 ± 2.2 (75% reduction). It should be noted that 0.5 mg/Kg is equivalent to the starting dose chosen for this Pilot study.
- Similar results were observed when CCL4-treated mice were exposed to either erlotinib or control vehicle.

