6.8.2.3 Factors

Stratification Factors: None

Descriptive Factor:

- Dose Level : +2 vs. +1 vs. 0 vs. -1 vs. -2

Grouping Factor:

- Dose escalation/de-escalation cohort vs. Dose expansion cohort
- Cohort: Surgical vs. Non-surgical

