13.8 Evaluation of Response

Minimal Effective Dose (MED) determination (using dose levels defined in section 5.1)

In addition to assessment of responses discussed below, the dose-escalation/de-escalation decision will also depend on safety, see Section 7.3.

Ten participants will be enrolled at the starting dose level (dose level 0) and if at least 2 in the first 5 evaluable participants have a response (40%) and the dose level is deemed to be safe, 10 participants will be enrolled at the next lower dose level (-1). If at least 2 participants have a response in the first 5 evaluable at this dose level and this dose level is deemed to be safe, 10 participants will be enrolled at the next lower dose level (-2). If at least 2 responses are observed at this dose level as well (in the first 5 evaluable) and this dose level is deemed to be safe, then this dose level will be considered the observed MED for this study, and further study will be warranted at this dose level.

At dose level 0, if fewer than 2 responses are observed (in the first 5 evaluable participants) and the dose level is deemed to be safe, 10 participants will be enrolled at the next higher dose level (+1). If at least 2 participants have a response in the first 5 evaluable at this dose level and the dose level is deemed to be safe, this dose level will be declared the MED and further study with this dose will be warranted. If fewer than 2 responses (in the first 5 evaluable) are observed at this dose level, 10 participants will be enrolled at the next higher dose level (+2). If at least 2 responses are observed (in the first 5 evaluable participants) at this dose level and the dose level is deemed to be safe, this dose

level will be declared the MED and further study with this dose will be warranted. If fewer than 2 responses are observed at this dose level (in the first 5 evaluable participants), we may consider including additional dose levels to find the MED for this study.

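### Section 13.5 tests biomarker changes across ordered dose levels only with an omnibus ANOVA, although the Section 1 objectives ask for a relationship with dose; an ordered analysis should be added

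*Combined protocol and SAP*

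**What the plan says.** Section 13.5 describes three analyses of the translational biomarkers: baseline values compared across dose levels, change from baseline by the Wilcoxon signed-rank test, and a plan to "compare these changes across dose levels using ANOVA (or the nonparametric equivalent"). Graphs across dose levels are added. Categorical variables get chi-square or Fisher's exact tests, which also ignore order. The section labels the results exploratory or hypothesis generating, and sets no alpha, power or effect size for them.

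All four translational objectives in Section 1 are worded as a relationship with dose-schedule, for example "Determine the relationship between erlotinib dose-schedule and gene expression signature associated with prognosis in cirrhosis participants". The endpoint lists in 1.3, 8.3 and 13.5 keep a dose relationship for three of the four. The viral-load endpoint there asks only whether erlotinib is associated with a reduction.

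Section 6.8.2.3 lists the levels in order ("Dose Level : +2 vs. +1 vs. 0 vs. -1 vs. -2"), and 5.1 gives them as 25, 50, 75, 100 and 150 mg/day. Section 13.3 sizes the trial "assuming the theoretical maximum of 3 dose levels", aims "to reach the goal of 5 evaluable participants in each dose level", and adds an expansion at the MED, "thus leading to 10 evaluable participants". Section 2.3 reports rat data: "The reduction of DEN-induced fibrogenesis associated with erlotinib was dose-dependent".

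No trend test, dose contrast or regression on dose is specified. The nearest item is in Section 3: a correlation of plasma level with phospho-EGFR reduction, to be used if the dose relationship proves inconsistent.

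**The concern.** An F test or Kruskal-Wallis test returns the same p-value if the dose labels are shuffled. It answers whether the levels differ somehow, not whether the biomarker moves with dose, in which direction, or how fast. Section 1 asks the second question. Section 13.4 says the translational results will help plan a larger study, and for that purpose a slope with an interval is more useful than an omnibus p-value.

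With about five evaluable participants per level, power is also short. A test that spends two degrees of freedom on any pattern is weaker than a one-degree-of-freedom trend test when the response is roughly linear. What is at stake is the usefulness of the exploratory dose-response results. The MED decision is not affected, because it rests on phospho-EGFR response and safety.

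**Working it through.** **The plan's own figure.** Nothing is stated for this comparison. The nearest operating figure is in 13.4, for the primary endpoint: P(at least 2 of 5 at a true rate of 60%) = 1 − 0.4⁵ − 5(0.6)(0.4⁴) = 1 − 0.010 − 0.077 = 0.913. This matches the stated 91%.

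**Inputs from the plan.** At most three levels; 5 evaluable each; 5 + 10 = 15 at the MED; 25 in total (all from 13.3).

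**Assumptions, because the plan gives none.** Two-sided 0.05, normal changes with SD 1, equally spaced level scores (−1, 0, 1), and a lowest-to-highest difference of 1.0, 1.5 or 2.0 SD. Both tests use the within-level error.

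**Formulas.**
- ANOVA: noncentrality λ = Σ nᵢ(μᵢ − μ̄)², with μ̄ the weighted mean; noncentral F on (k − 1, N − k) df.
- Trend: δ = Σ nᵢ(xᵢ − x̄)μᵢ / √Σ nᵢ(xᵢ − x̄)²; noncentral t on N − k df.

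**Worked example.** For 5/5/5 with a linear response of 0, 0.75, 1.5: λ = 5(0.75² + 0 + 0.75²) = 5.625. Also δ = 5(1.5)/√10 = 2.372, so δ² = 5.625. The signal is the same, but ANOVA must exceed F(2,12) = 3.885 while the trend test must exceed t(12) = 2.179. Power is 44.9% against 58.7%.

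**Linear response, ANOVA vs trend**

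| Evaluable per level | 1.0 SD | 1.5 SD | 2.0 SD |
|---|---|---|---|
| 5/5/5 | 22.1% vs 30.7% | 44.9% vs 58.7% | 70.2% vs 82.7% |
| 5/5/15 | 36.8% vs 48.1% | 70.8% vs 81.8% | 92.6% vs 96.9% |
| 5/15/5 | 24.3% vs 32.7% | 49.5% vs 62.1% | 75.6% vs 85.6% |

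At five per level the gain is 9 to 14 points. Over all three layouts it runs from 4 (5/5/15 at 2.0 SD) to 14.

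**Other shapes at 1.5 SD, ANOVA vs trend**

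| Shape | 5/5/5 | 5/5/15 | 5/15/5 |
|---|---|---|---|
| Plateau (0, 1.5, 1.5) | 57.0% vs 58.7% | 70.8% vs 70.9% | 70.8% vs 62.1% |
| Threshold (0, 0, 1.5) | 57.0% vs 58.7% | 87.6% vs 89.7% | 70.8% vs 62.1% |
| Umbrella (0, 1.5, 0) | 57.0% vs 5.0% | 70.8% vs 11.1% | 87.6% vs 5.0% |

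For example, the plateau at 5/15/5 has μ̄ = 1.2, so λ = 5(1.2²) + 20(0.3²) = 9.0, but δ² is only 5.625. The trend test leaves the rest of the signal unused. At 1.0 SD, the largest plateau or threshold gain with 15 at an end level is 5 points (52.3% vs 57.6%).

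**Two levels.** The two tests coincide: 54.9% each at 5 vs 5 and 78.4% each at 5 vs 15 (1.5 SD). Section 13.8 allows this path: if 75 mg/day misses the response rule and 100 mg/day is safe and meets it, then "this dose level will be declared the MED and further study with this dose will be warranted".

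**Scores.** With actual mg values for 75/100/150, a plateau at 5/5/5 gives 57.0% vs 47.8%, so the choice of score must be fixed in advance.

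**Rank versions** (5,000 simulated trials per setting, 5/5/5, 1.5 SD), Kruskal-Wallis vs a Jonckheere-type test: linear 40% vs 54%, plateau 51% vs 45%, umbrella 51% vs 1%.

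**The case against.** The strongest reply is that these analyses are declared exploratory, carry no alpha or decision rule, and already include plots in which a trend would show. That stands, and it limits the severity. It does not remove the mismatch with Section 1, because plots give no slope or interval.

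Four stronger readings are tempting, and the documents do not support them.

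- *ANOVA throws power away at no benefit under any monotone response.* A plateau is monotone, and the tables show gains from about 2 points down to a 9-point loss there. ANOVA also keeps sensitivity to an umbrella shape. Nor does Section 2.3 rule out a plateau. It reports dose-dependence for fibrogenesis and the gene signatures, but as printed it gives a single tumour count (5.0 ± 2.2) for both 2 and 0.5 mg/kg.
- *Every translational endpoint is a dose relationship.* That is true of the Section 1 objectives. It is not true of the viral-load endpoint in 1.3, 8.3 and 13.5, which is a before/after question suited to the signed-rank test.
- *The signed-rank test can never reach 0.05.* Run within one level of five, its smallest two-sided p is 2/2⁵ = 0.0625. But 13.5 does not say that it is run per level, and five is the target for primary-endpoint evaluability, not a stated limit for the translational data.
- *One regression of post/pre change fits everything.* It does not. Plasma erlotinib has no meaningful baseline, because prior erlotinib is excluded (4.2.1). Section 9.1 also defines signature suppression as a yes/no call on the day 7 specimen.

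**Conclusion.** The point holds as a minor one. Section 13.5 plans no analysis that uses dose order, while Section 1 asks for dose relationships. Adding one gives a direction, a slope and an interval. It also gives about 9 to 14 points more power if the response is roughly linear over three levels of five, with a range of 1.0 to 1.5 SD.

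That power gain rests on assumed effect size, SD, alpha, normality and layout; the plan states no values for the first four. The gain disappears with two levels. It is near zero for most plateau or threshold layouts and reverses with 15 at the middle level. Appendix E (Stage 5) sends the expansion to the middle level when 50 mg/day passes and 25 mg/day is safe but not effective, so that layout can occur. For these reasons the ordered analysis belongs beside the ANOVA, not in place of it. No stated figure, MED decision or primary analysis changes.

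**What to change.** In 13.5, keep the ANOVA (or rank equivalent) and the plots, and pre-specify an ordered analysis for the dose-relationship endpoints:

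- **Staining markers (phospho-ERK, PCNA, EGF, αSMA):** regress change from baseline on dose level, with the level scores stated in advance, and report slope and confidence interval. Jonckheere-Terpstra is the rank version.
- **Plasma erlotinib:** regress the post-dose level itself on dose.
- **Gene-signature call:** use an ordered test for proportions, such as Cochran-Armitage.
- **Viral load:** state that the signed-rank test is pooled over doses for the before/after question.

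The text should also say that with only two levels the trend test and the ANOVA are the same test.

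The cost is SAP wording, with no added participants, samples or procedures. The downsides are one more exploratory test per biomarker and a trend test that is weaker for plateau or non-monotone shapes. The retained ANOVA and plots cover those shapes.
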